### **2.2.1 Randomization and drug dispensing irregularities**

Inclusion is used here in place of randomization given these are open label, ascending dose studies. Inclusion and drug-dispensing irregularities occur whenever:

1. An inclusion is not in accordance with the protocol-defined inclusion method, such as a) an ineligible patient is included, or b) a patient is included twice.

OR

2. A patient is dispensed an IMP kit not allocated by the protocol-defined method, such as a) a patient at any time in the study is dispensed a different treatment kit than as assigned (which may or may not contain the correct-as-included IMP), or b) a non-included patient is treated with IMP reserved for included patients.

Inclusion and drug-dispensing irregularities will be monitored throughout the study and reviewed on an ongoing basis.

All inclusion and drug-dispensing irregularities will be documented in the clinical study report. If the number of irregularities is large enough to make a tabular summary useful, the irregularities will be categorized and summarized among included patients (number and percentages).

Inclusion and drug-dispensing irregularities to be prospectively identified include but are not limited to:

**Table 6 - Inclusion and drug allocation irregularities**

---

Kit dispensation without IVRS/IWRS transaction
Erroneous kit dispensation
Kit not available
Inclusion by error
Patient included twice
Patient switched to another site

---

## 2.3 ANALYSIS POPULATIONS

The all treated population comprises any patient with a signed informed consent and received at least one dose of the IMP.

### 2.3.1 Pharmacokinetic, pharmacodynamics and immunogenicity population

The PK population will consist of all patients in the safety population with at least one post-dose, non-missing serum concentration value.

The PD population will consist of all patients in the safety population with at least one post-dose biomarker assessment.

The ADA population will consist of all patients in the safety population with at least one post-dose, evaluable ADA sample.

In all cases, patients will be analyzed according to the treatment actually received.

### 2.3.2 Safety population

The safety population will consist of all patients who received at least 1 dose or part of a dose of the IMP, analyzed according to the treatment actually received

In addition:

- Patients for whom it is unclear whether they took the IMP will be included in the safety population according to the assigned treatment
- In case a patient receives 1 or more incorrect dose of sarilumab other than the one assigned, the dose regimen cohort allocation for as-treated analysis will be the dose regimen cohort in which he/she was treated for the longest duration.

### 2.3.3 Efficacy populations

The efficacy population will consist of all patients who received at least 1 dose of sarilumab. All patients should be followed at least to the end of the 12 week study treatment period and will be analyzed according to the treatment that they actually receive.

## 2.4 STATISTICAL METHODS

In general, summaries will be by study [REDACTED] except for the modeling of the PK data.

### 2.4.1 Demographics and baseline characteristics

Continuous data will be summarized using the number of available data, mean, standard deviation (SD), median, minimum, and maximum. For blood pressure, the average of the two SBP and the two DBP readings for a patient will be used for analysis. Categorical and ordinal data will be summarized using the number and percentage of patients.

Parameters described in [Section 2.1.1](#) will be summarized for the all treated population by dose regimen cohort, overall and within each weight group.

Medical and surgical history will be summarized by dose regimen cohort, overall and within each weight group, according to primary SOC and PT, sorted by internationally agreed order of SOC and decreasing frequency of PT within SOC (based on the overall cohort in each study).

P-values for demographic and baseline characteristic data will not be calculated.

No specific description of the safety parameters will be provided at baseline. If relevant, the baseline values will be described along with each safety analysis.

### 2.4.2 Prior or concomitant medications

The prior and concomitant medications will be presented for the all treated population as

- Prior medications discontinued before the first dose of IMP
- Prior medications that continued at the time of the first dose of IMP
- Concomitant medications.

Medications will be summarized by dose regimen cohort, overall and within each weight group, according to the WHO-DD dictionary, considering the first digit of the anatomic category (ATC) class (anatomic category) and the generic names. Sorting will be by decreasing frequency of anatomic category followed by all other generic names based on the overall incidence in the total cohort, for each study separately. In case of equal frequency regarding anatomic categories

(respectively generic names), alphabetical order will be used. All ATC codes corresponding to a medication will be summarized, and patients will be counted once in each ATC category (anatomic) linked to the medication. Therefore patients may be counted several times for the same medication.

The following summaries will also be provided:

- Vaccines (prior and concomitant, separately)
- Concomitant non-biological DMARDs (MTX, sulfasalazine [SSZ], leflunomide [LEF], hydroxychloroquine [HCQ]), folic acid, NSAIDs, and corticosteroids
- Prior DMARDs (biological and non-biological) taken since diagnosis of JIA and discontinued before the first dose of IMP

### **2.4.3 Extent of investigational medicinal product exposure and compliance**

The extent of IMP exposure and compliance will be assessed and summarized by actual IMP dose regimen cohort, overall and within each weight group, using the safety population ([Section 2.3.2](#)).

#### **2.4.3.1 Extent of investigational medicinal product exposure**

The extent of IMP exposure will be assessed by the duration of IMP exposure, and actual dose information.

The duration of sarilumab exposure is defined as: last dose date – first dose date + 14 days (+ 7 days for dose regimen 3 cohort). These calculations are regardless of unplanned intermittent discontinuations (see [Section 2.5.3](#) for calculation in case of missing or incomplete data).

Duration of IMP exposure will be summarized descriptively as a quantitative variable (number, mean, SD, median, minimum, and maximum) and categorically by numbers and percentages of patients within each of the following categories and cumulatively according to these categories:

- 12-week core part
  - $\leq 6$  weeks
  - $>6$  and  $\leq 12$  weeks
  - $>12$  weeks
- Final study data, including extension
  - $\leq 12$  weeks (3 months)
  - $>12$  and  $\leq 24$  weeks
  - $>24$  and  $\leq 36$  weeks
  - $>36$  and  $\leq 48$  weeks

- >48 and  $\leq$  72 weeks
- >72 and  $\leq$  96 weeks
- >96 and  $\leq$  120 weeks
- >120 and  $\leq$  144 weeks
- >144 and  $\leq$  156 weeks
- >156 weeks

Additionally, the cumulative duration of treatment exposure, defined as the sum of patients' duration of treatment exposure expressed in patient years, will be provided.

The time between doses will be summarized.

#### **2.4.3.2 Compliance**

A given administration will be considered noncompliant if the patient did not take the planned dose of IMP as required by the protocol. No imputation will be made for patients with missing or incomplete data.

**Percentage of compliance** for a patient will be defined as the number of administrations that the patient was compliant divided by the total number of administrations that the patient was planned to take on or before the last dose date during the treatment epoch defined in [Section 2.1.4](#).

Treatment compliance will be summarized descriptively as a quantitative variable (number, mean, SD, median, minimum, and maximum), along with a summary of the percentage of patients whose compliance is <80%. In addition, patients with the wrong dose will be summarized.

Overdose is defined as administering at least twice the assigned dose during an interval of less than 11 days for q2w dosing and less than 6 days for qw dosing. Symptomatic overdose will be reported as an AESI. More generally, dosing irregularities will be as listed in [Section 2.2.1](#).

#### **2.4.4 Analyses of pharmacokinetic variables**

Serum trough concentrations of functional sarilumab will be summarized using descriptive statistics (including number, arithmetic and geometric means, SD, standard error of the mean (SEM), CV (%), minimum, median, and maximum) by dose regimen cohort, overall and by weight group, for each visit. The samples will be considered non-eligible for these analyses if the previous dosing time is <11 days or >17 days before the sampling time for every other week regimens; <5 days or >9 days before the sampling time for every week regimens. Concentrations below the lower limit of quantification (LLOQ) will be set to zero for samples at predose (Week 0). Other concentrations below LLOQ will be replaced by LLOQ/2. Semi-log plots of concentration over time will also be provided (no value at time 0). Serum concentrations of

functional sarilumab will be summarized using the descriptive statistics mentioned above by immunogenicity status for each dose regimen cohort at each visit.

Listings of serum concentration will be provided for each individual patient including subject identification (ID), gender, age, first dose date, visit number, categorized time point (0 for trough level and 1 for pre-dose), date/time of previous dose, PK sampling date/time, duration since first dose (days), duration since previous dose (dd:hh), and serum concentration (mg/L).

All PK analyses will be performed using the PK population.

[REDACTED]

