9 ASSESSMENT OF INVESTIGATIONAL MEDICINAL PRODUCT

9.1 PHARMACOKINETICS PRIMARY ENDPOINT

The primary endpoint is: sarilumab PK exposure (maximum serum concentration observed [C_{max}] and area under the serum concentration versus time curve using the trapezoidal method during a dose interval [$AUC_{0-\tau}$]), following the first dose, concentration observed before treatment administration during repeated dosing (C_{trough}) from baseline to Week 12.

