9.1.1 Sampling time

For Group A patients (≥ 30 kg), blood for sarilumab PK sampling will be collected at Visit 2* (Day 1, prior to IMP administration), Visit 3 (Day 3), Visit 4 (Day 5), Visit 5 (Day 8), Visit 6 (Day 12), Visit 7 (Week 2)*, Visit 8 (Week 4)*, Visit 10 (Week 8)*, and Visit 12 (Week 12)*.

For Group B patients (< 30 kg and ≥ 10 kg) enrolled in the dose-finding and second portions, in order to minimize the amount of blood withdrawn, patients will be randomly assigned to sarilumab PK sampling schedule 1 or 2 with the following time points:

- Schedule 1: Visit 2* (Day 1), Visit 3 (Day 3), Visit 5 (Day 8)**, Visit 7 (Week 2)*, Visit 8 (Week 4)*, Visit 10 (Week 8)*, Visit 12 (Week 12)*
- Schedule 2: Visit 2* (Day 1), Visit 4 (Day 5), Visit 6 (Day 12), Visit 7 (Week 2)*, Visit 8 (Week 4)*, Visit 10 (Week 8)*, Visit 12 (Week 12)*.

The sampling schedule for blood collection in 12-week core treatment phase and the extension phases can be found in the study flow charts (see [Section 1.2.1](#) and [Section 1.2.2](#), respectively). For patients for whom the dose will be adjusted to the selected dose regimen, additional PK sampling will be collected for 12 weeks. The sampling schedule for blood collection in these patients can be found in the study flow chart in [Section 1.2.2.2](#).

For patients enrolled in the third portion, the PK sampling visits, ie, Visits 3, 4, 5, and 6 are not applicable during the core treatment phase. The sampling schedule for blood collection in these patients during the extension phase can be found in the study flow chart in [Section 1.2.2.3](#).

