10.3.1 Temporary treatment discontinuation with investigational medicinal product(s)

Temporary treatment discontinuation decided by the Investigator corresponds to more than one injection not administered to the patient.

Temporary treatment discontinuation may be considered by the Investigator because of suspected AEs. For laboratory abnormalities, Investigator will refer to [Appendix G](#) for the stopping rules. Re-initiation of treatment with the IMP will be done under close and appropriate clinical/and or laboratory monitoring once the Investigator will have considered according to his/her best medical judgment that the responsibility of the IMP(s) in the occurrence of the concerned event was unlikely and if the selection criteria for the study are still met (refer to [Section 7.1](#) and [Section 7.2](#)).

For all temporary treatment discontinuations, duration should be recorded by the Investigator in the appropriate pages of the CRF (see [Appendix G](#) for the stopping rules).

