11.4.3 Analyses of safety data

Safety data will be summarized descriptively. The summary of safety results will be presented by dose regimen. Further subdivision by weight group will be performed only for selected parameters given the small sample size. Additional methods including the approach to handle the dose-adjustment in safety analyses, safety analyses by time periods, and the exposure-adjusted analyses on safety events will be detailed in the statistical analysis plan.

The safety analysis will be based on the reported AEs and other safety information, such as clinical laboratory data, vital signs, etc. Safety and acceptability assessments (local tolerability) are the primary objectives of the extension parts of the studies (see [Section 9.3](#)).

All safety analyses will adhere to Sanofi “Guideline for the Analysis and Reporting of Safety Data from Clinical Trials.”

Observation period

The observation period will be divided into 5 epochs: Screening, Treatment in core period, Treatment in extension period, Follow-up, and Post-study (defined below):

- The **Screening** epoch is defined as the time from the signed informed consent date up to the time prior to the first dose of IMP.
- The **Core-treatment** epoch is defined as the time from the first dose of IMP to last dose in the core treatment phase + 13 days (or + 6 days for patients on weekly dosing), or first dose of IMP in the extension period for patients who enter the extension phase.
- The **Extension treatment** epoch is defined as the time from first dose of IMP in extension period to last dose of IMP in extension period + 13 days (or + 6 days for patients on weekly dosing). Only patients who enter the extension period have the **Extension treatment** epoch.
- The **Follow-up treatment** epoch is defined as the time from the EOT epoch (ie, the end of **core-treatment** epoch for patients not entering in the extension period; or the end of the **extension treatment** epoch for patients who enter the extension period) to last dose of IMP + 60 days.
- The **Post-study epoch** is defined as the time after the last dose of IMP + 60 days. The rationale of having “last dose of IMP + 60 days” as the end of **follow-up** epoch is to capture the events observed within approximately 5 half-lives of the last IMP.

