11.4.4 Analyses of pharmacokinetic and pharmacodynamics variables

Pharmacokinetic (PK) analyses will be performed using the PK population via pooling all available data.

Serum trough concentrations of functional sarilumab will be summarized using descriptive statistics (including number, arithmetic and geometric means, standard deviation, standard error of the mean (SEM), CV, minimum, median, and maximum) by dose, overall and by weight group, for each visit. The samples will be considered non eligible for these analyses if the previous dosing time is <11 days or >17 days before the sampling time for q2w regimens; <5 days or >9 days before the sampling time for qw regimens. Concentrations below the lower limit of quantification (LLOQ) will be set to zero for samples at predose (Week 0). Other concentrations below LLOQ will be replaced by LLOQ/2. Semi log plots of concentration over time will also be provided (no value at time 0). Serum concentrations of functional sarilumab will be summarized using descriptive statistics mentioned above by immunogenicity status for each dose at each visit (see [Section 9.1](#) and [Section 9.7](#)).

A PopPK model will be developed using [REDACTED] to describe the PK profile of sarilumab. A PopPK model will be used to estimate population and individual PK parameters, the sources of PK variability and assess the influence of covariates on PK parameters. The potential covariates to be evaluated in the PopPK analysis include [REDACTED]

[REDACTED] The predicted individual sarilumab PK exposure (C_{max} and $AUC_{0-\tau}$) following the first dose will be summarized using descriptive statistics by dose and weight group. PopPK results may be presented in a separate document from the CSR.

Serum concentrations of IL-6, total sIL-6R α and hs-CRP will be summarized using descriptive statistics (including number, arithmetic and geometric means, standard deviation, standard error of the mean [SEM], CV, minimum, median, and maximum) by dose and weight group for each visit ([Section 9.1](#) and [Section 9.7](#)).

[REDACTED]

[REDACTED]

[REDACTED]

[REDACTED]

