### 2.1.3 Pharmacokinetic variables

The primary endpoint is sarilumab PK exposure ( $C_{\max}$  and  $AUC_{0-\tau}$ ), following first dose, and  $C_{\text{trough}}$  from baseline to week 12.

The PK blood samples will be collected before IMP injection at a given visit according to the schedules of sample collection and at or near the onset and completion of the occurrence of a serious adverse event (SAE). Details can be found in Section 1.2 Study Flow Charts of the protocols [REDACTED]

In the extension part, the main PK parameter will be serum sarilumab  $C_{\text{trough}}$ .

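### The Ctrough eligibility rule checks only the last dosing interval, so troughs after earlier missed, held or incomplete doses count as eligible once one dose has been given on time

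*SAP*

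**What the plan says.** Ctrough from baseline to Week 12 is part of the primary endpoint. Protocol 9.1 defines it as "concentration observed before treatment administration during repeated dosing". For the extension, SAP 2.1.3 goes further: "In the extension part, the main PK parameter will be serum sarilumab" Ctrough.

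For the by-visit trough summary, SAP 2.4.4 sets one eligibility condition for q2w: "The samples will be considered non-eligible for these analyses if the previous dosing time is <11 days or >17 days before the sampling time". For qw the limits are "<5 days or >9 days before the sampling time for every week regimens". Protocol 11.4.4 repeats the rule: "The samples will be considered non eligible for these analyses if the previous dosing time is <11 days or >17 days before the sampling time".

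No readable text asks whether the doses before the last one were given, or whether any dose was complete. The PK population (SAP 2.3.1) needs only one post-dose concentration. The PK listing in SAP 2.4.4 shows the previous dose but no earlier history. Time between doses (SAP 2.4.3.1) and compliance (SAP 2.4.3.2) are summarised separately, with no link to trough eligibility.

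Interrupted dosing is foreseen. Protocol 10.3.1 states: "Temporary treatment discontinuation decided by the Investigator corresponds to more than one injection not administered to the patient". Protocol 10.3.3 withholds dosing until a confirmatory laboratory result is available.

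**The concern.** A trough at Week 8 or 12 is read as the level reached under repeated dosing with the regimen. After a gap, the earlier doses have partly washed out, and one on-time dose does not restore the accumulated level. The rule cannot see this, because the only interval it measures is on time. The sample is then averaged with fully accumulated troughs in the same visit row.

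An incomplete dose leaves no gap at all, so a timing rule cannot find it at any visit.

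At stake is the observed Ctrough table. Protocol 11.4.4 specifies a summary of model-predicted exposure only for first-dose Cmax and AUC. In the readable text, the observed table is therefore the only by-visit description of Ctrough. The dose-finding cells hold about six evaluable patients each, so one or two affected children can move a mean.

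**Working it through.** The plan states no figure for this effect, so there is none to reproduce.

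**Inputs**

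- Eligibility windows: 11-17 days (q2w) and 5-9 days (qw), from SAP 2.4.4 and Protocol 11.4.4.
- Core-phase trough visits: Weeks 2, 4, 8 and 12 (Protocol 9.1.1).
- Half-life: not given in the readable text. Protocol 11.4.3 explains the 60-day follow-up as meant "to capture the events observed within approximately 5 half-lives of the last IMP", which implies 60/5 = 12 days. I use 4 to 16 days as an assumed range.
- Cell sizes: 6 evaluable patients per regimen and weight group in dose finding, and 18 per weight group at the selected regimen (Protocol 6.1).
- Assumed: linear one-compartment decline, equal doses, absorption ignored, first dose always given.

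**Step 1: which patterns pass the rule**

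If the dose just before the sample is missed, the gap is 28 days for q2w (over 17) or 14 days for qw (over 9), and the sample is excluded. Missed doses therefore cannot affect Week 2, nor Week 4 for q2w. Other patterns pass if the last dose was on time:

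- q2w, one miss: 2 of 3 patterns at Week 8 and 4 of 5 at Week 12.
- q2w, two misses: 1 of 3 at Week 8 and 6 of 10 at Week 12.
- qw, one miss: 2 of 3 at Week 4, 6 of 7 at Week 8 and 10 of 11 at Week 12.

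**Step 2: size for one child**

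With r = exp(−ln2 × τ / t½), the trough is proportional to the sum of r^j over the doses given, where j counts dosing intervals back from the sample.

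q2w, t½ = 12 days: r = exp(−0.6931 × 14/12) = 0.44545. At Week 12 with six doses, the sum is 0.44545 + 0.19843 + 0.08839 + 0.03937 + 0.01754 + 0.00781 = 0.79699.

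- Week 8 missed: (0.79699 − 0.19843)/0.79699 = 0.751. Passes.
- Weeks 6 and 8 missed: (0.59856 − 0.08839)/0.79699 = 0.640. Passes.
- Week 10 missed: (0.79699 − 0.44545)/0.79699 = 0.441. Excluded by the rule.
- For reference, a trough after a first dose is 0.44545/0.79699 = 0.559 of the full Week 12 trough.

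qw, t½ = 12 days: r = 0.66742. With twelve doses, the sum is 0.66742 × (1 − 0.00781)/(1 − 0.66742) = 1.9911.

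- Week 10 missed: (1.9911 − 0.4454)/1.9911 = 0.776.
- Weeks 9-10 missed: 0.627. Weeks 8-10 missed: 0.527. All three pass.

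Over the assumed half-lives, as a percentage of the full-dosing trough:

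| Eligible pattern | 4 d | 8 d | 12 d | 16 d |
|---|---|---|---|---|
| q2w, Week 8 sample, Week 4 missed | 92 | 79 | 74 | 73 |
| q2w, Week 12 sample, Week 8 missed | 92 | 79 | 75 | 75 |
| q2w, Week 12 sample, Weeks 6 and 8 missed | 91 | 73 | 64 | 61 |
| qw, Week 4 sample, Week 2 missed | 79 | 73 | 72 | 73 |
| qw, Week 12 sample, Week 10 missed | 79 | 75 | 78 | 80 |

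Older misses fade. At 12 days, a q2w miss at Week 4 or Week 2 leaves the Week 12 trough at 95% or 98%.

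**Step 3: size for a cell**

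One affected child with ratio ρ multiplies the geometric mean by ρ^(1/n).

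- n = 6: 0.75^(1/6) = 0.953 and 0.64^(1/6) = 0.928, a fall of about 5% to 7%.
- n = 18: 0.75^(1/18) = 0.984 and 0.64^(1/18) = 0.976, a fall of about 1.6% to 2.4%.

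**The case against.** The existing rule removes the worst case, and Week 2 and q2w Week 4 troughs cannot be affected by missed doses. That stands and sets the scope. A reader might infer that any trough after a missed dose is accepted. The rule does not allow that.

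A reader might also infer that the primary PK result as a whole is biased. The documents do not support this. Protocol 9.1.4 lists Ctrough among parameters calculated with the population PK model. A model fed with actual dosing records would not carry the bias, although the readable text does not say that it uses them. The end of SAP 2.4.4 is redacted, so more may be specified there.

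A third tempting reading is that holds are commoner at higher exposure, so that differences between regimens are flattened. That is speculation. Protocol 10.3.1 allows restart only when the investigator thinks it unlikely that the drug caused the event and the selection criteria are still met. Protocol 10.3.2 lets an interruption over 31 days be treated as permanent if efficacy suffers. The q2w case with Weeks 6 and 8 missed leaves 42 days between doses. Two or three missed qw doses leave only 21 or 28 days. Core-phase q2w injections are given at the site by a professional caregiver, which makes casual misses less likely. Nor does the text say that this table decides the dose: the Dose Escalation Committee weighs PK, PD, efficacy and safety together.

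Finally, analysing patients as treated makes a trough as delivered a legitimate description. Dropping held patients could itself select on exposure. Both points are fair, and they argue for showing two versions rather than replacing one with the other.

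**Conclusion.** The gap is real but narrow. As written, the rule counts core-phase troughs at Weeks 8 and 12 (q2w) and Weeks 4, 8 and 12 (qw) as eligible after earlier missed or held doses, if the last dose was on time. It does not check for incomplete doses at all. For an affected child, the observed Ctrough understates the value expected under the regimen:

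- q2w at Week 12: about 75% with Week 8 missed (75-92% for half-lives of 4-16 days), and about 64% with Weeks 6 and 8 missed (61-91%).
- qw at Week 12: about 75-80% after one miss before the last dose.

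The effect on a cell mean is modest in the dose-finding cells and small at n=18, unless several children are affected. These sizes rest on linear one-compartment decline and an inferred half-life; nonlinear kinetics would change them. Incomplete doses were not sized. The frequency of holds is not given, so the total bias cannot be stated, and I make no claim about differences between regimens.

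**What to change.** In SAP 2.4.4 and Protocol 11.4.4, derive a dosing-history flag for each timing-eligible trough. Set it when a dose was missed or not given in full among the preceding three scheduled doses (q2w) or the doses due in the preceding four weeks (qw). Then:

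- show the by-visit Ctrough summary twice, with all timing-eligible samples and with flagged samples excluded;
- state the number flagged in each regimen, weight group and visit cell;
- add the flag to the PK listing.

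At a 12-day half-life, a single miss just outside these windows changes the Week 12 trough by 0.03937/0.79699 = 4.9% (q2w, Week 4) or 0.13243/1.9911 = 6.7% (qw, Week 7), so little is left unflagged.

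The cost is a wording change and one variable derived from dosing data already needed for the compliance summary. The restricted table loses some samples, expected to be few, and may be selective if holds are related to exposure. That is why both versions should be shown. No dosing or clinical rule changes.
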